Describe the schedule, payment method, and payment total of any reimbursement that research participants will receive for participation in the research (e.g., gift cards or cash with amount, etc.)

Compensation for Research Related Injury

Describe who will pay for the costs of medical treatment and/or compensation in the event of a research related injury:

Funding agency is providing some/all payment for injury

Funding agency is providing no payment for injury

N/A

Provisions to Monitor the Data to Ensure the Safety of Research Participants

1. Describe how often the data will be monitored for completeness, accuracy and adherence to the protocol.

Every quarter, the PI will review protocols to make sure they are being adhered to and spot check data collection.

2. Indicate if there will be a Data and Safety Monitoring Board or Committee:
- There will **not** be a formal Data and Safety Monitoring Board/Committee.
 - There will be a formal Data and Safety Monitoring Board/Committee.

Provide information about the DSMB/C including the contact information of the committee member(s) (as applicable); whether it is independent from the study sponsor; how often it meets; the type of data that will be used; written reports, etc.

Community-Based Participatory Research

- This is **not** a community-based participatory research project – please leave the rest of this section blank
- This is a community-based participatory research project
 The LGBT Center has been integral in the development of this design and will be a full partner in carrying out the work. Their staff is currently training on CREC and will be added when that is complete. A coordinator is being hired with the expectation they will also be a research partner. They will be involved in analysis and dissemination.

Note: Community based research is research that is conducted as an equal partnership between academic investigators and members of a community. In Community Based Participatory Research (CBPR) protects, the community participates fully in all aspects of the research process.

MULTI-SITE RESEARCH (when UH or CWRU is the IRB of Record)

Does this project have multiple sites?

- Yes
- No – please leave the rest of this section blank

Non-Local Site Information for Multi-Site Studies

If this is a multi-site study where you are the **lead investigator**, list the following information for each relying site:

1. Name of site:
2. PI of relying site:
3. Name of IRB contact:
4. Phone number of IRB contact:
5. Email address of IRB contact:

Non-Local Recruitment Methods for Multi-Site Studies

If this is a multi-site study and research participants will be recruited by methods **not under the control of the local site** (e.g. call centers, national advertisements) describe those methods. Local recruitment methods are described above.

1. Describe when, where, and how potential research participants will be recruited.

2. Describe the methods that will be used to identify potential research participants.
3. Describe the materials that will be used to recruit research participants.

Multi-Site Research Communication Plan (when you are the lead investigator)

If this is a multi-site study where you are the **lead investigator**, describe the processes to ensure communication among sites including:

- All sites will have the most current version of the protocol, consent document, and HIPAA authorization
- All required approvals (initial, continuing review and modifications) have been obtained at each site (including approval by the site's IRB of record)
- All modifications have been communicated to sites, and approved (including approval of the site's IRB of record) before the modification is implemented
- All engaged participating sites will safeguard data, including secure transmission of data, as required by local information security policies
- All engaged participating sites will safeguard data, including secure transmission of data, as required by local information security policies
- All local site investigators conduct the study in accordance with applicable federal regulations and local laws
- All non-compliance with the study protocol or applicable requirements will be reported in accordance with local policy

If this is a multi-site study where you are the **lead investigator**, describe the method for communicating to engaged participant sites the following:

1. Problems:
2. Interim results:
3. The closure of the study:

Additional Information

If you have any additional information regarding your study not covered in the template, please include it here.

References

- Alpert, A. B., CichoskiKelly, E. M., & Fox, A. D. (2017). What lesbian, gay, bisexual, transgender, queer, and intersex patients say doctors should know and do: A qualitative study. *Journal of Homosexuality*, 64(10), 1368-1389. doi:10.1080/00918369.2017.1321376

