RESEARCH QUESTION: Do interactive dialogues between trans and gender nonconforming (TGNC) - trained in health literacy and advocacy - and healthcare providers and staff seeking cultural competency around TGNC primary care result in 1) more confidence on the part of TGNC in navigating the healthcare system, 2) more confidence on the part of providers in responding to the needs of TGNC patients, (sub question – is there a measurable difference between types of providers’ responses to trainings, i.e., medical doctors compared to nurse practitioners) 3) person-to-person networks between the two populations resulting in ongoing, sustainable dialogue, 4) TGNC individuals prepared to train other TGNC in a peer-to-peer role to act as advocates on behalf of the TGNC population within the healthcare system, all of which ultimately result in increased access to and use of primary care services and reduce the health disparities faced by TGNC individuals?

Background

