Study Design

Non-random participatory action research consisting of discussion groups and facilitated meetings

Study Procedures

Over the course of the grant year, each step of the project is divided into three month portions. The first quarter will be dedicated to recruiting and forming a

cohort of TGNC individuals, drawn mostly from the LGBT Center’s extensive contact lists and centrality within the TGNC population. We plan on recruiting 20 individuals to ensure we meet the minimum retention of 12 subjects throughout the study needed for qualitative saturation (Guest, Bunce, and Johnson 2006), and individuals between 14-18 years of age will be able to participate with guardian permission. Interested individuals will fill out applications to identify their interests and ability to commit to the project and will allow us to create a cohort that reflects the diversity of the TGNC community in Cuyahoga County, including gender identity, types of gender-affirmative care required (including whether or not someone is considering, in the process of, or completed physical transition), racial and ethnic identity, age (over 14), and socio-economic class. Upon accepting the invitation to participate, each member of the cohort will complete a pretest that will elicit data on their experiences in the healthcare system, their knowledge of basic and transgender-specific medical terminology, their familiarity with healthcare providers in Cuyahoga County, and the likelihood of seeking care under a number of conditions (acute, chronic, moderate, severe). We expect this to take one month. The following two months will consist of meeting as a cohort twice a month. The first two meetings will be dedicated to understanding the group’s collective experiences with health care, what they would like to see change, and what strategies can be used to accomplish those ends. We recognize that TGNC people come from a variety of backgrounds and each will bring their own strengths, networks, and perspectives to the table which will allow us to make full use of the indigenous expertise of the group. In consultation with the Nursing School of CWRU, we will develop a health literacy training that meets the expressed needs of the cohort and [name] will present it during the 3rd meeting. The goal here is not to provide all possible health education but rather to arm the cohort with the skills and language to empower them to act as advocates on their own behalf when navigating the healthcare system. The final meeting (the 4th) in this first quarter will be with a trained facilitator ([name]) who will, under the direction of the TGNC cohort, plan a series of three interactive dialogues between the TGNC cohort and the healthcare providers. By meeting with the TGNC cohort first, without the healthcare providers, the TGNC cohort will have the opportunity to ensure the dialogues are designed to meet their objectives. Individual healthcare practitioners and medical staff will be recruited during the first quarter from the aforementioned clinics. We will recruit at least twelve providers and twelve staff members, who will attend one meeting each. All of the clinics we have documented support from and those we are in current dialogue with have previously reached out to the LGBT Center for training in this area, and CMEs may be available through MetroHealth. In the second quarter, we will

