
conduct a pretest that will collect data on attitudes towards TGNC individuals, TGNC-specific healthcare concerns, depth and breadth of referral networks for TGNC providers. Once the healthcare provider group is solidified, the LGBT Center will host three evening meetings (once per month) with the trained facilitator wherein TGNC individuals lead a conversation about what they see as barriers to their care, how they would like to be treated, and what they want healthcare providers to know about them as people. The first two meetings will be with healthcare practitioners and the final meeting will be medical staff so that the meetings can be more specific and without the interference of power dynamics within the provider groups. Healthcare providers and staff will only attend one meeting each. During this second quarter, the TGNC cohort will continue to meet on its own once a month to debrief from meetings, respond to what they have learned so far, and possibly refine the strategies for future meetings with healthcare providers as the series goes forward. At the end of the three months of dialogue, each participant, from both the TGNC cohort and healthcare provider, will be given a post-test to measure changes in attitude, practice, and knowledge. Participants will also have the opportunity to engage in a reflective interview. The third quarter will diverge onto two different paths: the LGBT Center project coordinator will continue to engage with the cohort as they shift into the role of peer educators and advocates with other members of the TGNC community that interact at the LGBT Center. [name] will conduct follow-up interviews with any TGNC cohort member that notifies the researchers that they have sought medical care and with any healthcare provider that notifies the researchers that they have had a clinical interaction with a TGNC individual. We will not be seeking any protected medical information or the identity of patients, in the case of healthcare providers, but rather a discussion of the ease or difficulty in communication, levels of comfort, and comparison with other interactions in general. Throughout the process, both [name] and the LGBT Center coordinator will be engaged in participant observation (Bernard, 2002; Denzin & Lincoln, 1994) and keep detailed field notes on all the meetings. All participant observation will take place during the scheduled cohort meetings which will not be recorded except through note-taking. All interviews will be transcribed unless the participant chooses not to be recorded; interviews and field notes will be coded with a priori codes (Bernard & Ryan, 2010) derived from the literature on reducing health disparities and TGNC-specific health care by a research assistant. Participants may choose to participate in an optional reflective interview where they are asked to reflect on the appropriateness and effectiveness of the project in meeting their expectations. Pre- and post-tests will be analyzed to determine the success of facilitated dialogue in improving confidence and knowledge by both the TGNC

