
cohort and the healthcare providers, and depending on sample size, we will determine if there are any statistically significant changes. This analysis and write up will encompass the last quarter of the project.

Study Timeline

	Pre-Screening	Meetings 1-18	Facilitated meetings	Optional interviews
Estimated time requirement of visit for TGNC cohort	Fill out on own	1.5 hours		1.5 hours
Estimated time requirement of visit for medical providers			2 meetings, 1.5 hours each	1.5 hours
Estimated time requirement of visit for medical staff			1 meeting, 1.5 hours	1.5 hours

Devices

If the research involves device(s), describe your plans to use the device(s).

N/A

ClinicalTrials.gov Information

Case Western Reserve University Protocol Record IRB-2018-2194, TRANSLATE: Transgender and Gender Nonconforming Individuals' Access to Healthcare, has been reviewed and will be made public on ClinicalTrials.gov.

List of Data to be Collected

Note: If using REDCap, all selected identifiers below must be indicated as PHI.

1. *Indicate what identifiers you will collect*
 - Name
 - Address (e.g., Zip code, other geographical designation, etc.)
 - Dates related to an individual (e.g., Date of admission, birth, surgery, etc.)
 - Telephone number
 - Fax number
 - Email address
 - Social security number
 - Medical record number
 - Health plan beneficiary number
 - Account number
 - Certificate/license number
 - Any vehicle or other device serial
 - Device identifiers or serial numbers
 - Web URL
 - Internet protocol (IP) address
 - Finger or voice prints

- Photographic images
- Other: Any characteristic that would uniquely identify the individual

2. List all other data to be collected for the research study (e.g. laboratory values, physician notes, length of stay, etc.)

Data Analysis Plan

Pre and post tests will analyze knowledge gained. Qualitative data analysis with atlas.TI will be performed on field notes based on meeting observations and any optional interviews completed.

Confidentiality of Data

1. To maintain the confidentiality of the data:
 - I will use a unique study identifier (not derived from the participants personal identifiers) to code individuals' data and I will store this ID log separate from study data.
 - Other (please explain) Upon completion of the study, identifiers will be destroyed, leaving only the unique coded identifier in fieldnotes and transcripts. Voice recordings will be destroyed as soon as interviews are transcribed.

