upfront about the possibility of breach of confidentiality and encourage those who feel it could adversely impact their lives severely not participate. As far as the data collection goes, we will store all fieldnotes, audio recordings, surveys, and any other data collected on Box, a secure, encrypted server. Access to the data will be limited to the PI, co-PI, community partner (to be hired), and the RA ([name]).

2. If applicable, indicate which experimental procedures may have risks to the research participants that are currently unforeseeable.
 - N/A
3. If applicable, describe the risks to others who are not research participants.
 - N/A
4. Describe the availability of medical or psychological resources that research participants might need.
 - N/A

The LGBT Community Center maintains contacts with May Dugan for crisis intervention and other community support, so if someone needs assistance, that connection can be made quickly.

Provisions to Protect the Privacy Interests of Research Participants

We will encourage confidentiality among participants in group settings but also be upfront about the fact that this is not a guarantee of confidentiality. We will not use identifiable information in any reports or publications. Interviews will be held privately.

Potential Benefit to Research Participants

- There is potential benefit to research participants.
 1. Describe the potential benefits that individual research participants may experience from taking part in the research. Include the probability, magnitude, and duration of the potential benefits.

TGNC participants will be offered training on medical literacy to increase their own knowledge of the medical system. Medical providers will be offered training on cultural competency to increase their own knowledge of how to treat TGNC patients. These benefits could make navigating the space easier for each set of individuals.
- There is **no** direct benefit to research participants.
 2. If no direct benefit, state the potential benefit to society or others. **By reducing stigma and increasing knowledge about TGNC concerns, the medical profession can reduce the health disparities faced by TGNC people.**

Withdrawal of Research Participants

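### In the TGNC cohort the pre/post change spans the whole programme, so it cannot show the success of the facilitated dialogues

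*Combined protocol and SAP*

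**What the plan says.** Study Procedures sets the TGNC baseline at enrolment: "Upon accepting the invitation to participate, each member of the cohort will complete a pretest". The listed content is healthcare experiences, medical terminology, familiarity with local providers, and likelihood of seeking care.

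Four cohort meetings follow in the first quarter. Two cover shared experiences and strategies, the third is the health-literacy training, and the fourth plans the dialogues with the facilitator. The training has this stated goal: "arm the cohort with the skills and language to empower them to act as advocates on their own behalf when navigating the healthcare system". In its section on potential benefit, the plan adds: "TGNC participants will be offered training on medical literacy to increase their own knowledge of the medical system".

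In the second quarter there are three monthly dialogues, and "the TGNC cohort will continue to meet on its own once a month to debrief from meetings". One post-test closes the three months. Study Procedures then says the pre- and post-tests will be analysed "to determine the success of facilitated dialogue in improving confidence and knowledge", and it names both the TGNC cohort and the providers. The Data Analysis Plan says only "Pre and post tests will analyze knowledge gained".

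The second-quarter baseline is to "conduct a pretest that will collect data on attitudes towards TGNC individuals", along with referral networks. By its content it is the provider and staff instrument.

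**The concern.** A before/after difference measures everything that happens between the two tests. Here that includes a training session intended to raise knowledge, two peer meetings and a planning meeting, all before the cohort meets a provider. The tests are still assigned to judge the dialogues.

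Followed as written, the plan would report a gain produced by the training or the peer meetings as a success of the dialogues. The risk-benefit section hopes the intervention can be reproduced elsewhere. A group wishing to do so could not tell from the cohort's scores whether the dialogue phase added anything.

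**Working it through.** The plan states no test, alpha, effect size, SD or power for this contrast, so there is no figure to reproduce. The check is a count, a comparison of outcomes, and an illustration.

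**1. What lies between the two TGNC tests** (Study Procedures)

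| Component | Contacts |
|---|---|
| Peer meetings (1st and 2nd) | 2 |
| Health-literacy training (3rd) | 1 |
| Planning with the facilitator (4th) | 1 |
| Facilitated dialogues | 3 |
| Monthly debriefs | 3 |
| Total | 10 |

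- First quarter: 2 months × 2 meetings = 4, all before the first dialogue (4/10).
- Second quarter: 3 dialogues + 3 debriefs = 6.
- Dialogues are 3/10 of the full window and 3/6 of the window after the fourth meeting.

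The Study Timeline and the compensation section mention up to 18 meetings without placing the others, so the count covers only contacts whose timing is described. It does not measure each contact's share of any effect.

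**2. Do the training and the tests overlap?**

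- Knowledge: the pretest covers medical terminology, and the training is meant to supply skills and language. The benefit section expects training to raise knowledge. The overlap is direct.
- Confidence: the first aim in the Research Question is confidence in navigating the healthcare system, and the training's stated goal is self-advocacy in that same setting. The overlap is by stated purpose, because confidence is not among the listed pretest contents.

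**3. Could the change be significant with no dialogue effect?**

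Assumptions: a paired t test at two-sided 5%, a dialogue-phase effect of zero, and a training effect of d SDs of the change score. The probability of a significant gain is P(T > t(0.975, n−1)), where T is noncentral t with n−1 degrees of freedom and noncentrality d√n. The sample sizes are the plan's own: 20 recruited and a minimum of 12 retained. The critical values are 2.093 (n=20) and 2.201 (n=12).

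| Assumed d | n=20: d√n | Probability | n=12: d√n | Probability |
|---|---|---|---|---|
| 0.3 | 1.34 | 25% | 1.04 | 16% |
| 0.5 | 2.24 | 56% | 1.73 | 35% |
| 0.8 | 3.58 | 92% | 2.77 | 71% |

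These are not type I error rates, because the score really did change. They are the chances that a real change would be credited to the wrong component.

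**4. Precision of any mean change**

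The 95% CI half-width in SDs of the change score is t(0.975, n−1)/√n:

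- n=20: 2.093/√20 = 0.47
- n=12: 2.201/√12 = 0.64

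**The case against.** The strongest reply is that this is one loose sentence in a plan that elsewhere describes a package. The Research Question asks "Do interactive dialogues between trans and gender nonconforming (TGNC) - trained in health literacy and advocacy - and healthcare providers and staff", which can be read as making training part of what is studied. The justification for excluding non-English speakers calls the primary intervention a discussion-based group, and the Data Analysis Plan does not mention dialogue. On a whole-programme reading an enrolment baseline is the right one. That stands, and it is why rewording alone would remove the unsupported claim. It does not rescue the sentence in Study Procedures. The plan uses the word dialogues for the three meetings with providers, held with a cohort that has already been trained.

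Two objections to the numbers also have force. The planning meeting and the debriefs serve the dialogues, so on a broad view 7 of the 10 contacts belong to the dialogue process (1 + 3 + 3). The probabilities rest entirely on assumed training effects. Neither point changes the finding, because the training and the two peer meetings still fall inside the window.

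A second baseline would not isolate dialogue either, since debriefs, elapsed time and repeat testing remain. That is correct, and the label proposed for it says so. Field notes and reflective interviews may suggest which stage helped, but the plan assigns this inference to the tests, and qualitative data do not alter what the contrast measures.

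**Conclusion.** The concern holds and should be fixed. For the TGNC cohort, post-test minus enrolment pretest estimates an uncontrolled change over cohort meetings, training, dialogues and debriefs. The attribution to facilitated dialogue is not supported.

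This follows from the schedule alone. It depends neither on the illustrative effect sizes nor on the exact number of meetings. The evidence of overlap is strongest for knowledge; for confidence it rests on matching stated aims. Providers and staff are pretested in the second quarter and do not receive the cohort's training, so the point does not extend to them.

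**What to change.** 1. **Reword the analysis sentence in Study Procedures.** For the TGNC cohort, define post-test minus enrolment pretest as the uncontrolled change over the whole programme: cohort meetings, health-literacy training, dialogues and debriefs. This alone removes the unsupported claim and costs only a text edit.

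2. **Repeat the same questionnaire at the end of the fourth cohort meeting.** Report post-test minus this second baseline, with a 95% CI, as the uncontrolled change over the dialogue phase (dialogues plus debriefs). State that it excludes the training but does not separate dialogue from debriefs, time or repeat testing. The cost is one more questionnaire at a meeting already scheduled, with some extra burden and a possible practice effect from a third exposure to the same items.

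### As described, the care-seeking item covers neither routine visits nor care setting, so a change in care-seeking could not be tied to primary care

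*Combined protocol and SAP*

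**What the plan says.** The research question lists four nearer results: confidence among TGNC participants, confidence among providers, networks between the two groups, and TGNC members ready to train peers. It then adds "all of which ultimately result in increased access to and use of primary care services", together with reduced health disparities.

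Study Procedures describes the TGNC pretest in one sentence with four domains. The domain on care-seeking is "the likelihood of seeking care under a number of conditions (acute, chronic, moderate, severe"). Members complete the pretest on accepting the invitation, before the cohort meetings start.

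The post-test comes at the end of the three months of dialogue. Participants are "given a post-test to measure changes in attitude, practice, and knowledge". The text does not say whether it repeats the pretest items.

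Actual care is touched on only in the third quarter, through "follow-up interviews with any TGNC cohort member that notifies the researchers that they have sought medical care".

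**The concern.** The research question names a specific kind of care, whereas the care-seeking item, as described, asks about care in general. Its labels classify an illness by course and severity. They do not reach the person who is well and decides whether to book a check-up or screening, which is a core part of primary care. They also do not record whether someone who would seek care would go to a primary care clinic, an emergency department, a specialist or a gender clinic.

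At stake is what the study can say about the last part of its own question. If members reported more willingness to seek care after the dialogues, the data would not show what kind of care they meant. If the change lay mainly in routine visits, the listed conditions give it no obvious place to appear. A baseline question left out of the pretest cannot be recovered once the meetings have begun.

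**Working it through.** No arithmetic applies: the documents give no power, effect size or error rate for this outcome. The check sets each described data source against two features needed to link care-seeking to primary care: (a) routine or preventive care, and (b) the setting where care would be sought.

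1. **Pretest care-seeking item (Study Procedures).** The labels are acute, chronic, moderate and severe. Routine or preventive: 0 of 4. Setting: not named.
2. **Other TGNC pretest domains (Study Procedures).** One is meant to "elicit data on their experiences in the healthcare system", one covers medical terminology, and one covers "their familiarity with healthcare providers in Cuyahoga County". Experience is general and past, and knowing of a provider is not the same as intending to go there. Neither (a) nor (b) is described.
3. **Post-test (Study Procedures).** It covers attitude, practice and knowledge. Practice is the nearest term, but it is not defined for TGNC members, and the same words cover the healthcare providers. Neither (a) nor (b) is described.
4. **Third-quarter follow-up interviews (Study Procedures).** These reach only "any TGNC cohort member that notifies the researchers that they have sought medical care". They cover medical care of any kind and depend on the member coming forward. Their stated content is communication, comfort and comparison with other encounters. Neither (a) nor (b) is described.
5. **Optional reflective interviews (Study Procedures).** These ask whether the project was appropriate and effective in meeting expectations. Neither (a) nor (b) is described.
6. **Field notes (Study Procedures and Data Analysis Plan).** These record what is said at meetings. Primary care may come up, but nothing says that (a) or (b) will be recorded for each member.

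Result: none of the six sources is described as recording (a) or (b).

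The analysis text does not close the gap. Study Procedures directs the pre/post comparison at confidence and knowledge, and the Data Analysis Plan at knowledge gained. Neither mentions care-seeking.

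The consequence can be seen with two members who both become more willing to seek care for a chronic condition. One would go to a primary care clinic and the other to an emergency department. On the item as described, they give the same answer.

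**The case against.** The strongest reply is that the questionnaire is not in the documents. The protocol gives a one-sentence summary of its domains, and the words in parentheses may only indicate how the scenarios vary. The actual form may already ask about check-ups and about setting. This stands as a limit: the point applies to the measure as described, and if the form already covers both features, a sentence saying so settles it.

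Second, chronic and moderate conditions are often handled in primary care, so the item is not uninformative. That is fair. But without a question on setting the answers cannot be attributed to primary care, and preventive visits are still not covered.

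Third, primary care use is a downstream result, and the planned analysis concerns confidence and knowledge. The protocol elsewhere speaks of health care in general when describing benefits. This lowers the weight of the point but does not remove it, because primary care is named in the research question itself.

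Three stronger readings are tempting, and the documents do not support them:

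- **That the item is the study's proxy for primary care use.** The protocol never gives it that role.
- **That answers would be mis-scored, or distorted in a total score.** No scoring, change score or total is described, and the item is described only for the pretest.
- **That the severe scenarios would already be near their ceiling at baseline.** No baseline figures are given, and the response may be graded.

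**Conclusion.** The point holds as a gap in coverage. As described, the care-seeking item includes no routine or preventive visit and no setting, its repetition in the post-test is not stated, and no other described source fills the gap. The study could therefore not tell whether a change in care-seeking concerned primary care.

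This rests on the protocol's summary of the pretest being a fair account of its content. It has no numerical size.

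A reader might infer that repairing the item would let the study show that the dialogues increase primary care use. It would not. Stated intention is not use. The design is non-random, with no comparison group described, and the cohort is 20 people, with at least 12 to be retained for qualitative saturation. The repair would let the study describe intention toward the kind of care it asks about. It is a cheap improvement and does not correct an error that undermines the study.

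**What to change.** Before the pretest is given:

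- Add at least one routine scenario, such as a check-up or screening.
- For every scenario, add a tick-box for where the person would go: primary care, urgent or emergency care, a specialist or gender clinic, or nowhere.
- State that the post-test repeats the same items in the same form.
- In the Data Analysis Plan, state that the change will be reported descriptively, scenario by scenario, as intention to use primary care and not as evidence of actual use.

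If the existing form already has these items, saying so in Study Procedures is enough, together with the statements on the post-test and on reporting. The cost is a few extra minutes per participant at each test, for a cohort of 20. The intervention and the meeting schedule do not change.
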